1 PROTOCOL REVISION HISTORY

| Date/Name | Description |
|-----------------------------------|---|
| 14June2018 by [name] | 
Final Protocol, Amendment 1
 
Following review by the Institutional Review Board, this protocol is being amended to provide justification for the use of a placebo-control design. In addition, information on safety measures that will be undertaken by the Investigators should there be clotting in the extracorporeal circuit has been added.
 
Thus, Section 8.4.1 Rationale for this Study and Study Design, Section 8.5 Risks and/or Benefits to Patients, and Section 11.3 Early Termination of Patients from the Study were updated. Section 13.3 Hemodialysis Procedure and Blood Clots in the Dialyzer Cartridge was created.
 
In addition, the following changes were made:
 
 - Section 11.2 Exclusion criteria, criterion 2 was updated (changes in strikethrough and additions in bold): “With the exception of unfractionated heparin during HD, Econcomitant or prior use of anticoagulant/antiplatelet agents (e.g., low molecular weight heparins, warfarin, apixaban, bivalirudin, ticagrelor, edoxaban, dabigatran, rivaroxaban, clopidogrel, prasugrel, ticlopidine, eptifibatide, tirofiban, dipyridamole, diclofenac, and all other NSAIDs) that may affect hemostasis for 2 weeks prior to check-in on Day -8 and throughout the study.” - Section 11.2 Exclusion criteria, criterion 3 was updated (changes in strikethrough and additions in bold): “Use of unfractionated heparin for HD sessions from check-in on Day -8 and throughout the study.” - Section 11.2 Exclusion criteria, criterion 9: The value for hemoglobin concentration at screening was increased from 8.5 g/dL to 10 g/dL. The hemoglobin limit was increased to allow for the possibility of blood loss of up to 228 mL if there is a clot in the dialyzer circuit. Also, the 5 other clinical laboratory values had no specific timing on when these values were required; thus, “at screening” was added for these clinical laboratory tests. - Section 13.6 Dialysate Analysis; this section was added as samples of the dialysate will be taken for future analysis (e.g., assessment of urea or drug level in the dialysate). Samples will be stored for up to 5 years). |

| | |
|----------------------------------|---|
| | 
- Section 13.7.1 Blood Sampling and Processing, wording was added that leftover samples would be stored for up to 5 years. 
Updates in blood volume (i.e., correction in number of samples were made increasing the total blood volume by about 5 mL (from 430 mL to 435.9 mL)
 
Minor editorial, consistency, and formatting updates were made throughout the protocol.
 |
| 25May2018 by [name] | Final Protocol |

5 SYNOPSIS

| | |
|--------------------------|--|
| Compound: | xisomab 3G3 (anti-factor [F] XI monoclonal antibody, IgG4) |
| | Active ingredient: xisomab 3G3 (~15 mg/mL) Excipients: 8% sucrose, 10 mM histidine, 30 mM arginine HCl, 10 mM methionine, 80 ppm polysorbate 80 |
| Clinical Indication: | Prevention or treatment of thrombotic and thromboembolic diseases |
| Study Phase: | Phase 2 |
| Study Objectives: | 
The primary objective of this study is:
 
 • To assess the safety and tolerability of a single dose of xisomab 3G3 when injected through a port into the proximal (arterial) dialysis line immediately after initiation of a hemodialysis (HD) procedure in patients with end stage renal disease (ESRD). 
The secondary objectives of this study are:
 
 • To assess the pharmacodynamics (PD) of a single dose of xisomab 3G3 when injected through a port into the proximal (arterial) dialysis line immediately after initiation of a HD procedure in patients with ESRD. • To assess the efficacy of a single dose of xisomab 3G3 on HD efficiency when injected through a port into the proximal (arterial) dialysis line immediately after initiation of a HD procedure in patients with ESRD. • To assess the pharmacokinetics (PK) of a single dose of xisomab 3G3 when injected through a port into the proximal (arterial) dialysis line immediately after initiation of a HD procedure in patients with ESRD. |
| Summary of Study Design: | 
This is a phase 2, randomized, double-blind, placebo-controlled, single-dose study of xisomab 3G3 designed to evaluate the safety, efficacy/potency, and PK at 2 dose levels administered to patients with ESRD undergoing HD.
 
Patients will be enrolled into Cohort 1 or Cohort 2; cohorts will be dosed sequentially. Within a cohort, patients will be randomized to active drug or placebo as summarized below:
 |

| | Cohort | Treatment | Active:Placebo | Cohort Size | |
|--|---|-----------|----------------|-------------|--|
| 1 | Infusion dose of 0.25 mg/kg xisomab 3G3 or placebo | 2:1 | 9-12 | | |
| 2 | Infusion dose of 0.5 mg/kg xisomab 3G3 or placebo | 2:1 | 9-12 | | |
| 
This study includes a screening period of 28 days prior to checking-in to the clinical research unit on Day -8. From Day -7 (one week prior to dosing on Day 1) through Day -1, all patients will undergo HD 3 times and will be assessed for all scheduled procedures and endpoints before and after each HD session as per the Study Events Flow Chart (Section 6).
 
On Study Day 1, prior to dosing, patients will undergo baseline measurements followed by initiation of a regular HD procedure, consistently using only one type of dialyzer cartridge in each patients. Immediately after the start of blood perfusion, a single dose of xisomab 3G3 or matching placebo will be injected through a port into the flowing arterial blood in the proximal dialysis line. Patients will continue to undergo HD procedures and scheduled assessments from Day 1 through Day 12.
 
Study assessments will include physical examinations, vital signs, electrocardiogram (ECGs), clinical laboratory tests, HD vascular access site (AV fistula or AV graft) reaction, antibody titer (immunogenicity), adverse events (AEs), PD blood sampling (coagulation parameters), and PK blood sampling to be performed throughout the study according to the Study Events Flow Chart (Section 6). On Days -7, -5, and -3 and Days 1, 3, 5, and 12, bleeding time from the HD vascular access sites on the AV fistula or AV graft (ladder or buttonhole technique) will be evaluated at the end of the HD session. The dialyzer cartridge will be rinsed and visually inspected at the end of the HD procedure and graded against a standardized visual assessment scale. After visual assessment, the used and rinsed dialyzer cartridge will be frozen and saved for later retained content (deposited blood-derived material) analysis. The number of dialyzer cartridges used for the HD session will be recorded.
 
All patients who received the study drug or placebo (including patients who terminate the study early) will undergo follow-up procedures at the Clinical Research Unit (CRU) approximately 12 days after dosing.
 | | | | | |
| Number of Patients: | 
A total of up to 24 adult male and female patients will be enrolled; 9-12 patients are planned for each cohort.
 
In each cohort, an attempt will be made to enroll at least 50% of females and at least 30% of a race/ethnicity minority group. An
 | | | | |

| | |
|---|--|
| | attempt will also be made to approximately match key characteristics, including sex, average age, and weight per cohort. |
| Dosage, Dosage Form, Route, and Dose Regimen: | 
On Day 1, patients in each cohort will receive a single dose of xisomab 3G3 or placebo injection into the proximal (arterial) dialysis line on one occasion. Cohort 1 will be conducted prior to initiation of Cohort 2.
 
Planned doses will be as follows:
 
Cohort 1: 0.25 mg/kg xisomab 3G3 or matching placebo
 
Cohort 2: 0.5 mg/kg xisomab 3G3 or matching placebo
 |
| Key Assessments: | 
Safety
 
Safety assessment will include physical examinations, vital signs, ECGs, clinical laboratory tests, vascular access site reaction, bleeding time, and AEs.
 
Number/severity of AE will be tabulated and summary statistics for the 12-lead ECGs, vital signs, and clinical laboratory tests may be computed and provided, as deemed clinically appropriate.
 
Pharmacodynamics:
 
Efficacy/potency assessment will be measured as efficiency of the hemodialysis by assessing thrombus accumulation (ranked by visual inspection) in the dialyzer cartridge, protein accumulation in the HD filter, BUN and potassium blood levels, length of HD, measurement of urea removed by 3 hours of dialysis, and total dialysate urea (Kt/V and urea reduction ratio [URR]). Coagulation tests will also be performed.
 
Change from baseline will be summarized by treatment (2 active dose levels and pooled placebo) and per timepoints using descriptive statistics.
 
Pharmacokinetics:
 
The following PK parameters will be calculated for xisomab 3G3 in plasma, as appropriate: AUC_{0-t}, AUC_{0-inf}, AUC%extrap, C_{max}, T_{max}, K_{el}, t_{1/2}, CL, and V_{ss}.
 
PK parameters will be summarized by dose level using descriptive statistics.
 
Immunogenicity:
 
Development of antibodies against the study drug will be evaluated by determining the anti-drug antibody (ADA) titer.
 |

6 STUDY EVENTS FLOW CHART

| Study Procedures ^{a:} | Screening ^{b:} (Day -37 to Day -9) | Study Days | | | | | |
|--|---|-------------------|------------------|------------------|------------------|------------------|------------------|
| | | Evaluation Period | | | | | |
| | | -8 | -7 | -6 | -5 | -4 | -3 |
| | | HD ^{d:} | HD ^{d:} | HD ^{d:} | HD ^{d:} | HD ^{d:} | HD ^{d:} |
| Days → | C-I ^{e:} | start | end | start | end | start | end |
| HD → | | | | | | | |
| Hours → | | | | | | | |
| Administrative Procedures | | | | | | | |
| Informed Consent | X | | | | | | |
| Inclusion/Exclusion Criteria | X | X | | | | | |
| Medical History | X | | | | | | |
| Safety Evaluations | | | | | | | |
| Full Physical Examination ^{e:} | X | X | | | | | |
| Height | X | | | | | | |
| Weight | X | X | X ^{f:} | X ^{g:} | X | X ^{g:} | X |
| 12-Lead Safety ECG | X | X | | | | | |
| Vital Signs (HR, BP, RR, and T) | X | X | X ^{f:} | | X ^{f:} | | X ^{f:} |
| Bleeding of Access Site | | | | X ^{g:} | | X ^{g:} | |
| Hem, Serum Chem ^{h:} , and UA ^{i:} | X | X | | | | | X ^{g:} |
| Coagulation ^{j:} | X | | X ^{f:} | X ^{g:} | X ^{f:} | X ^{g:} | X ^{f:} |
| Platelet Count ^{s:} | | | X ^{f:} | X ^{g:} | X ^{f:} | X ^{g:} | X ^{f:} |
| Serum Pregnancy Test (♀ only) | X | X | | | | | |
| Serum FSH (PMP ♀ only) | X | | | | | | |
| Urine/Saliva Drug and Alcohol Screen | X | X | | | | | |
| HIV/Hepatitis Screen | X | | | | | | |
| AE Monitoring | | | | | X | | |
| ConMeds Monitoring | X | | | | X | | |
| Other Procedures | | | | | | | |
| Blood BUN and Potassium (for Kt/V and URR) ^{s:} | | | X ^{f:} | X ^{g:} | X ^{f:} | X ^{g:} | X ^{f:} |
| Dialysate Analysis | | | X ^{k:} | X ^{k:} | X ^{k:} | X ^{k:} | |
| Visual Assessment and Processing of Dialyzer Membrane | | | | X ^{l:} | | X ^{l:} | X ^{l:} |
| Confinement in the CRU | | | | | X | | |
| Visit | X | | | | | | |

| Study Procedures ^{a:} | Study Days | | | | | | | | | | | | | | | | | | | |
|--|-----------------|-------|-----------------|---|---|-----------------|---|---|---|----|----|----|-----------------|-----------------|-----------------|-----------------|-----------------|-----------------|-----------------|-----------------|
| | PK/PD Period | | | | | | | | | | | | | | | | | | | |
| | Days → | 1 | | | | | | | | | | 2 | 3 | | | 4 | 5 | | 6 | |
| Hours → | 0-0.016 | 0.167 | 0.5 | 1 | 2 | 3 | 4 | 6 | 8 | 12 | 16 | 24 | 48 | start | end | 72 | 96 | start | end | 120 |
| Safety Evaluations | | | | | | | | | | | | | | | | | | | | |
| Abbreviated Physical Examination ^{e:} | X ^{m:} | | | | | | | | | | | | | | | | | | X ^{p:} | |
| Weight | X ^{f:} | | | | | X ^{g:} | | | | | | X | | X ^{f:} | X ^{g:} | X | | X ^{f:} | X ^{g:} | X ^{p:} |
| 12-Lead Safety ECG | X ^{m:} | | | | | | | | | | | | | | | | | | X ^{p:} | |
| Vital Signs (HR, BP, RR and T) | X ^{m:} | | | X | | | | | | | | | X ^{f:} | | | | X ^{f:} | | X ^{p:} | |
| Bleeding of Access Site | | | | | | X ^{g:} | | | | | | | | | X ^{g:} | | | X ^{g:} | | |
| Hem, Serum Chem ^{h:} , and UA ^{i:} | X ^{m:} | | | | | | | | | | | | | | | | | | X ^{p:} | |
| Coagulation ^{j:} | X ^{f:} | | | | | X ^{g:} | | | | | | | X ^{f:} | X ^{g:} | | | X ^{f:} | X ^{g:} | X ^{p:} | |
| Platelet Count ^{s:} | X ^{f:} | | | | | X ^{g:} | | | | | | | X ^{f:} | X ^{g:} | | | X ^{f:} | X ^{g:} | | |
| AE Monitoring | | | | | | | | | | | | | X | | | | | | | |
| ConMeds Monitoring | | | | | | | | | | | | | X | | | | | | | |
| Study Drug Administration / PK/PD/Immunogenicity | | | | | | | | | | | | | | | | | | | | |
| Xisomab 3G3 Administration ^{n:} | X | | | | | | | | | | | | | | | | | | | |
| Blood for free xisomab 3G3 PK | X ^{o:} | X | X | X | X | X | X | X | X | X | X | X | X ^{o:} | | | X ^{o:} | | X ^{p:} | | |
| Blood for free xisomab 3G3 PD (aPTT) ^{s:} | X ^{o:} | X | X | X | X | X | X | X | X | X | X | X | X ^{o:} | | | X ^{o:} | | X ^{p:} | | |
| Blood for Immunogenicity | X ^{m:} | | | | | | | | | | | | | | | | | | | |
| Blood BUN and Potassium (for Kt/V and URR) ^{s:} | X ^{f:} | | | | | X ^{g:} | | | | | | | X ^{f:} | X ^{g:} | | | X ^{f:} | X ^{g:} | | |
| Dialysate Analysis | | | X ^{k:} | | | X ^{k:} | | | | | | | X ^{k:} | X ^{k:} | | | | | | |
| Visual Assessment and Processing of Dialyzer Membrane | | | | | | X ^{l:} | | | | | | | X ^{l:} | | | | X ^{l:} | | | |
| Other Procedures | | | | | | | | | | | | | | | | | | | | |
| Vascular Access Site Reaction | X ^{m:} | | | | | X ^{q:} | | | | | | | X ^{q:} | | | | X ^{q:} | | | |
| Confinement in the CRU | | | | | | | | | | | | | X | | | | | | | |
| Return Visit | | | | | | | | | | | | | | | | | | | | |

| Study Procedures ^{a:} | Study Days | | | | | | |
|---|------------------|-----------------|------------------|-----------------|------------------|-----------------|------------------|
| | Follow-up Period | | | | | | |
| | Days → | 7 | 8 | 9 | 10 | 11 | 12 |
| | HD → | | HD ^{d:} | | HD ^{d:} | | HD ^{d:} |
| | Hours → | | start | end | start | end | start |
| Safety Evaluations | | | | | | | |
| Abbreviated Physical Examination ^{e:} | | | | | | | X ^{r:} |
| Weight | | X ^{f:} | X ^{g:} | X ^{f:} | X ^{g:} | X ^{f:} | X ^{g:} |
| 12-Lead Safety ECG | | | | | | | X ^{r:} |
| Vital Signs (HR, BP, RR, and T) | | X ^{f:} | | X ^{f:} | | X ^{f:} | X ^{r:} |
| Bleeding of Access Site | | | | | | | X ^{g:} |
| Hem, Serum Chem ^{h:} , and UA ^{i:} | | | | | | | X ^{r:} |
| Coagulation ^{j:} | | | | | | X ^{f:} | X ^{g:} |
| Platelet Count ^{s:} | | | | | | X ^{f:} | X ^{g:} |
| Serum Pregnancy Test (♀ only) | | | | | | | X ^{r:} |
| AE Monitoring | | | | X | | | X |
| ConMeds Monitoring | | | | X | | | |
| Study Drug Administration / PK/PD/Immunogenicity | | | | | | | |
| Blood for free xisomab 3G3 PK | | | | | | | X ^{r:} |
| Blood for free xisomab 3G3 PD (aPTT) ^{s:} | | X ^{o:} | | X ^{o:} | | | |
| Blood for Immunogenicity | | | | | | | X ^{r:} |
| Other Procedures | | | | | | | |
| Blood BUN and Potassium (for Kt/V and URR) | | | | | | X ^{f:} | X ^{g:} |
| Dialysate Analysis | | | | | | X ^{k:} | X ^{k:} |
| Visual Assessment and Processing of Dialyzer Membrane | | | | | | | X ^{l:} |
| Return Visits | | | X | | X | | X |

- a: For details on Procedures, refer to [Section 13](#)
- b: Within 28 days prior to Day -8.
- c: Patients will be admitted to the CRU on Day -8, at the time indicated by the CRU and will remain confined up to Day 6 or prior early termination.
- d: Patients will undergo hemodialysis 3 times a week, on Day -7, Day -5, Day -3, and Day 1, Day 3, Day 5, Day 8, Day 10, and Day 12. For each patient, the hemodialysis will last at least 3 hours as per patient standard schedule which will be the same throughout the study.
- e: Symptom-driven physical examination may be performed at other times, at the PI's or designee's discretion.
- f: To be performed ~ 1 hour prior to the start of hemodialysis.
- g: To be performed at the end of hemodialysis.
- h: Samples for serum chemistry will be obtained following a fast of at least 4 hours, however, in case of dropouts or rechecks, patients may not have fasted for 4 hours prior to the serum chemistry sample is taken.
- i: For anuric patients, urinalysis may not be performed.
- j: Coagulation parameters (activated partial thromboplastin time [aPTT], prothrombin time [PT], and international normalized ratio [INR]).
- k: The dialysate sample will be taken at 30 minutes and at 3 hours after the start of hemodialysis. The dialysate will be freeze and sent to Aronora.
- l: To be performed when the dialyzer cartridge is removed and collected at the end of HD.
- m: To be performed prior to dosing.
- n: A single dose of xisomab 3G3 or matching placebo will be administered at Hour 0. The dose will be injected through a port into the flowing arterial blood in the proximal dialysis line according to the randomization schedule, immediately after the start of HD.
- o: When the PK or PD sample is on an HD day, the sample should be taken at least 1 hour prior the start of HD session. The actual time will be recorded.
- p: To be performed at discharge or early termination; the PK and aPTT should be taken at 120 hour postdose.
- q: The vascular access sites (AV fistula or AV graft puncture sites) are to be evaluated immediately after the end of HD and removal of the needles from the fistula or graft for bleeding cessation or other reactions.
- r: All patients who received the study drug or placebo (including patients who terminate the study early) will undergo follow-up procedures at the Clinical Research Unit (CRU) approximately 12 days after dosing, as they return for their last HD. Events performed on Day 12 can be performed at end of HD if more appropriate.
- s: Platelet count, BUN and potassium, and aPTT value will be taken from the hematology, serum chemistry, and coagulation sample, respectively, when these are scheduled to be collected at the same time. Samples will not be taken twice at a same timepoint.

Abbreviations: ♀ = Females, AE = Adverse events, BUN = Blood urea nitrogen, BP = Blood pressure, C-I = Check-in, Chem = Chemistry, ConMeds = Concomitant medication, CRU = Clinical research unit, ECG = Electrocardiogram, FSH = Follicle-stimulating hormone, FU = Follow-up, Hem = Hematology, HD = Hemodialysis, HIV = Human immunodeficiency virus, HR = Heart rate, Kt/V = ratio of volume of fluid completely cleared of urea, PD = Pharmacodynamic, PK = Pharmacokinetics, PMP = Postmenopausal, RR = Respiratory rate, T = Temperature, UA = Urinalysis, URR = Urea reduction ratio.

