10 STUDY DESIGN

10.1 Overall Study Design and Plan

This is a phase 2, randomized, double-blind, placebo-controlled, single-dose study of xisomab 3G3 designed to evaluate the safety, efficacy/potency, and PK at 2 dose levels administered to patients with ESRD undergoing HD.

A total of up to 24 adult male and female patients will be enrolled; 9-12 patients are planned for each cohort. In each cohort, an attempt will be made to enroll at least 50% of females and at least 30% of a race/ethnicity minority group. Patients will be enrolled into Cohort 1 or Cohort 2; cohorts will be dosed sequentially. Within a cohort, patients will be randomized to active drug or placebo as summarized below:

Table 2: Cohort and Treatment Randomization

| Cohort | Treatment | Active:Placebo | Cohort Size |
|--------|--|----------------|-------------|
| 1 | Infusion dose of 0.25 mg/kg xisomab 3G3 or placebo | 2:1 | 9-12 |
| 2 | Infusion dose of 0.5 mg/kg xisomab 3G3 or placebo | 2:1 | 9-12 |

This study includes a screening period of 28 days prior to checking-in to the clinical research unit on Day -8. From Day -7 (one week prior to dosing on Day 1) through Day -1, all patients will undergo HD 3 times and will be assessed for all scheduled procedures and endpoints before and after each HD session as per the Study Events Flow Chart ([Section 6](#)).

On Study Day 1, prior to dosing, patients will undergo baseline measurements followed by initiation of a regular HD procedure, consistently using only one type of dialyzer cartridge in each patient. Immediately after the start of blood perfusion, a single dose of xisomab 3G3 or matching placebo will be injected through a port into the flowing arterial blood in the proximal dialysis line. Patients will continue to undergo HD procedures and scheduled assessments from Day 1 through Day 12.

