## **8.4 Clinical Laboratory Tests (Serum Chemistry, Hematology, Coagulation and Urinalysis)**

Safety serum chemistry, hematology and urinalysis tests are performed at Screening, Day -8 check-in, Day 1 predose, Day 6 and Day 12. For anuric patients, urinalysis may not be performed. Platelet count are collected at start and end of HD on Days -7, -5, -3, 1, 3, 5 and 12 and on Day 6. Platelet count are collected at start and end of HD on Days -7, -5, -3, 1, 3, 5 and 12 and Day 6. aPTT results are presented and discussed in the PD Section 7.2.

Out-of-range values and clinically significant results will be listed.

For all numeric laboratory values, descriptive statistics will be presented for each laboratory test by assessment time point and treatment. Change from baseline will be summarized in a similar manner. Baseline is defined as the result closest and prior to

dose which may include unscheduled results. This will typically be the result collected at predose on Day 1. Postdose unscheduled events or early termination results will not be included in summaries.

For each laboratory test, a shift table will be developed to compare the frequency of the results at baseline (above normal, normal, or below normal) with the respective postdose results.

Coagulation parameters and platelet count will be listed and presented together since they have the same timepoints. Urinalysis test results will be listed only.

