### **8.5 Vital Signs**

Vital signs tests (HR, BP, RR and T) will be assessed at Screening, Day -8 check-in, start of HD on Days -7, -5, -3, 1, 3, 5, 8, 10 and 12, 1 hour postdose on Day1, Day 6 discharge or early term and Day 12 follow-up.

Vital sign results will be summarized by dose level, pooled placebo, and time point. Change from baseline will be summarized in a similar way. Baseline is defined as the result closest and prior to the dose on Day 1, which may include unscheduled results, whichever is later. Postdose unscheduled events or early termination results will not be included in summaries.

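### Day 12 hematology, serum chemistry and ECG may be taken before or after dialysis, yet are compared with a pre-dialysis baseline under a single unlabelled Day 12 time point

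*Protocol*

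**What the plan says.** **Timing on Day 12.** In the protocol's Study Events Flow Chart (Section 6), Day 12 hematology, serum chemistry, urinalysis and ECG carry footnote r alone. That footnote places follow-up at the last HD visit and adds: "Events performed on Day 12 can be performed at end of HD if more appropriate". Other Day 12 measures are fixed:

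- Coagulation, platelet count, BUN/potassium and weight are marked f (about 1 hour before HD) and g (end of HD).
- Access-site bleeding is marked g.
- Vital signs have one f reading and one r reading.

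**Baseline.** Protocol Section 10.1 sets the order on Day 1: "On Study Day 1, prior to dosing, patients will undergo baseline measurements followed by initiation of a regular HD procedure". The dose follows immediately after blood perfusion starts. SAP 8.4 takes the laboratory baseline as the last result before the dose and adds: "This will typically be the result collected at predose on Day 1". SAP 8.5 says: "Baseline is defined as the result closest and prior to the dose on Day 1", and SAP 8.6 uses the same rule for ECG. The baseline is therefore pre-dialysis.

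**Day 12 in the SAP.** SAP 8.4 lists Day 12 for hematology and chemistry with no dialysis qualifier, and SAP 8.6 lists a Day 12 follow-up ECG. Change from baseline is summarized for all three, and the laboratory tests also have shift tables. The table shells label rows by day and hour. SAP 8.12 fixes one footnote r item, the anti-drug antibody sample, at the end of HD.

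**The concern.** A sample taken after a dialysis session differs from one taken before it because solutes and fluid have been removed, whatever the study drug does. If some or all Day 12 samples are post-HD, the change from the pre-HD baseline contains that session effect, and nothing in the tables shows it.

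This matters because changes in ECGs and laboratory values, against both pre-treatment and placebo, are part of the primary outcome (Protocol 9.2, SAP 2.2). For these measures the only scheduled post-dose time points are Day 6 and Day 12. Day 6 is a non-dialysis day that follows the Day 5 session, so Day 12 before HD is the one scheduled post-dose point that can match the baseline state. Footnote r makes that match optional.

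Hemoglobin is a concrete case. Protocol 13.3 warns of up to about 228 mL of blood loss if the circuit clots and says hemoglobin will be followed more closely. Fluid removal concentrates the blood, so a post-HD hemoglobin on Day 12 could hide a fall.

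**Working it through.** The plan states no figure that depends on this point: Protocol 14.1 chose the sample size without statistical considerations. The check is a trace of each measure, followed by an illustration of size.

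**1. Which Day 12 summaries are exposed**

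| Measure | Day 12 timing (flow chart) | SAP summary | Exposed? |
|---|---|---|---|
| Hematology other than platelets | r only | change and shift | yes |
| Serum chemistry | r only | change and shift | yes (BUN and potassium also have fixed pairs, below) |
| 12-lead ECG | r only | change | yes |
| Vital signs | f and r | change; start of HD and follow-up are separate time points | only the r reading |
| Coagulation, platelets, BUN/potassium pairs, weight | f and g | times fixed | no |
| Physical examination, urinalysis | r | listed only | no change table |

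BUN is in the safety chemistry panel (Protocol 13.2.7). The shells drop time points already summarized as PD endpoints from Tables 14.3.5.5 and 14.3.5.6 (coagulation and platelets), but carry no such note for the chemistry tables.

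**2. Size of one session, using BUN**

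Inputs: Kt/V of at least 1.2 (inclusion criterion 1); t of at least 3 hours (protocol) or about 4 hours (SAP 9); UF/Wt of 0 to 0.04 (assumed). The formula is that of SAP 7.2.3 with a minus sign before the logarithm:

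Kt/V = −ln(R − 0.008t) + (4 − 3.5R) × UF/Wt, where R = post-HD BUN / pre-HD BUN.

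The sign as printed gives negative values, which cannot be squared with the 1.2 criterion. At R = 0.35, t = 4 and UF/Wt = 0.03 it gives −1.06; with the minus sign the result is 1.23.

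Solving for Kt/V = 1.2:

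- t = 3, UF/Wt = 0: R = e^(−1.2) + 0.024 = 0.325, a fall of 67.5%.
- t = 4, UF/Wt = 0.02: R = 0.350, a fall of 65.0%.
- t = 4, UF/Wt = 0.04: R = 0.368, a fall of 63.2%.

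The range is about 63% to 68%. At Kt/V of 1.4 to 1.6 it is 69% to 77%.

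**3. Effect on the summaries**

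- Within an arm, at a 65% fall, a post-HD share p gives a mean change of −65% × p from dialysis alone: 0% at p = 0, −32.5% at p = 0.5 and −65% at p = 1.
- Arm sizes: 2:1 in cohorts of 9 to 12 gives 6 to 8 per active dose. Pooled placebo is 2 × 3 = 6 to 2 × 4 = 8.
- Between arms, a two-patient imbalance gives 2/8 × 65% = 16% of baseline, or 2/6 × 65% = 22%.

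**4. How likely an imbalance is by chance**

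With independent binomial timing and the same post-HD share in both arms, the probability of a gap of at least two patients is:

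| Post-HD share | 6 per arm | 8 per arm |
|---|---|---|
| 50% | 0.39 | 0.45 |
| 25% or 75% | 0.31 | 0.38 |

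The share is an assumption, since the documents do not give one.

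**The case against.** The strongest reply is that the plan already protects much of Day 12, and that what is left may not bias the comparison with placebo.

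- **Scope.** A reader might infer that footnote r undermines every Day 12 safety measure. The documents do not support that. Vital signs have a fixed pre-HD reading that SAP 8.5 keeps as its own time point. Physical examination is listed only (SAP 8.8). Coagulation, platelets, weight and the BUN/potassium pairs have fixed times. This part of the objection stands.
- **BUN as the example.** A like-for-like pre-HD Day 12 BUN exists and is tabulated separately from the post-HD value. This also stands. BUN only illustrates how far a session can move a value in the safety chemistry table; hemoglobin, liver enzymes and QTcF have no such pair.
- **Differential bias.** A reader might infer a spurious between-arm difference of about 32% (4/8 × 65%). That needs four of eight patients sampled post-HD in one arm and none in the other. A gap of four or more in either direction has a probability of only about 0.08 with 8 per arm and a 50% share. Staff who evaluate safety are blinded (Protocol 12.4.1), and nothing shows that timing would follow treatment. The site may also sample everyone at end of HD, as SAP 8.12 does for antibodies. The between-arm artefact would then cancel, but the within-arm change and shift tables would still be displaced. Cohorts run in sequence with placebo pooled across them, so a drift in site practice need not cancel.
- **Reconstruction.** HD start and end times and ECG times are listed, so state can be recovered for ECGs. For laboratory values it is only partial: out-of-range tables show clock time, but the full laboratory listing shell has day, hour and date without it.

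**Conclusion.** The point holds for Day 12 hematology other than platelets, serum chemistry and 12-lead ECG, and for the second, flexible vital-sign reading. For these, following the plan as written can put a dialysis-session effect into the change from baseline and, for laboratory tests, into the shift tables, without any label. Between arms the effect disappears if timing is uniform or balanced; with 6 to 8 per arm and discretionary timing, balance is not assured.

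The BUN figures assume that the Day 12 session delivers the entry-level Kt/V, ultrafiltration of 0% to 4% of weight, and, for the chance calculation, independent timing at the shares shown. They should not be carried over to other analytes.

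The consequence is moderate. All summaries are descriptive, so no test or error rate is affected, and Protocol 8.4.1 puts the weight of the primary endpoint on adverse events. It is a worthwhile clarification at low cost. The documents do not support a claim that the safety comparison with placebo is invalid.

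**What to change.** Either of two changes is enough:

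1. In the flow chart, mark Day 12 hematology, serum chemistry and ECG with footnote f (about 1 hour before HD) and remove them from the permission in footnote r.
2. Keep the flexibility, but record a pre/post-HD flag for each of these measures. State in SAP 8.4 and 8.6 that only pre-HD Day 12 values enter the change-from-baseline and shift tables, with post-HD values listed. Treat the flexible Day 12 vital-sign reading in the same way.

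The cost is footnote wording or one data field. There is no extra visit, and pre-HD blood is already drawn on Day 12 for coagulation, platelets and BUN/potassium. The site loses a little scheduling flexibility on the last day. Under option 2, patients sampled only after HD drop out of the Day 12 change and shift tables.

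Neither option makes Day 12 fully comparable with baseline. With no Day 0, the Day 1 baseline falls 3 days after the previous session (Day −3), and Day 12 falls 2 days after Day 10. A table footnote should say so.
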